9.4.2. Efficacy Analyses

[figure not shown]
The efficacy endpoints will be analyzed using the ITT and the PP populations.

Response status per investigator's assessment will be categorized at each response assessment visit as CR, very good partial response (VGPR; only among subjects with WM), partial response (PR), minor response (MR; only among subjects with WM), stable disease (SD), progressive

disease, or not evaluable (NE) per published criteria for lymphoma (Cheson et al 2014, Owen et al 2013 for WM) and CLL (Hallek et al 2008, Cheson et al 2012). In the unlikely situation that the subject does not have any disease at baseline, the best response will be denoted as no disease (ND).

Best overall response is the best response recorded during the study treatment before and including the first progressive disease, in the order of CR, PR, SD, progressive disease, NE, and ND.

A subject is considered an objective responder if they have a best overall response of CR or PR for lymphoma or CR, VGPR, PR, or MR for WM. The ORR is the proportion of objective responders. Subjects who do not have sufficient baseline or on-study response assessment information to be adequately assessed for response status will be included in the denominators in the calculation of ORR. ORR will be estimated with 95% CI, which will be calculated based on the exact method for binomial distributions. Best overall response will also be summarized.

For subjects with CLL, changes in peripheral blood leukemic cells from baseline to each post-treatment assessment will be summarized with mean, median, standard error, and 95% CIs.

For subjects with measurable lesions, target lesion sizes will be measured by sum of product of diameters (SPD). The best percent change from baseline, defined as the largest decrease in SPD during study will also be summarized, and a waterfall plot of best percent change will be generated. Note that for subjects who only have increases in SPD from baseline, the smallest increase will be considered as the best change from baseline.

9.4.3. Safety Analyses

The clinical safety data (vital signs, ECGs, routine laboratory tests, physical examinations, and AEs) will be summarized using descriptive statistics (eg, mean, frequency) using the safety population.

Summary tables may be replaced with listings when appropriate. For instance, an AE frequency table may be replaced with a listing if it only contains a few unique preferred terms reported on

relatively few subjects. Unless otherwise stated, table summaries will be limited to AEs occurring within 30 days of the last administration of study medication.

9.4.3.1. Adverse Events

A treatment-emergent AE (TEAE) is any AE either reported for the first time or worsening of a pre-existing event after first dose of study drug. Analysis of AEs will be limited to TEAEs, but data listings will include all AEs regardless of their timing to study drug administration.

Unresolved missing onset date, causality, or severity will be handled according to the following rules:

- An unresolved missing causality will be considered treatment-related.
- An unresolved missing severity will be identified as an unknown severity.
- A unresolved missing onset date will be considered treatment-emergent, with the following examples illustrating exceptions:
 - If the stop/resolution date is before the first dose date on Day 1, then the AE will be considered as not being treatment-emergent.
 - If both the month and day are missing, and the last day of the year is before the first dose date on Day 1, then the AE will not be considered treatment-emergent.
 - If only the day is missing, and the last day of the month is before the first dose date on Day 1, then the AE will not be considered treatment-emergent.
 - If only the day is missing, and the first day of the month is after the first dose date on Day 1, then the AE will be considered treatment-emergent.

Adverse events will be coded to system organ class and preferred term using the Medical Dictionary for Regulatory Activities (MedDRA[®]) coding dictionary. Severity of AEs will be based on the NCI CTCAE version 4.03.

The subset of AEs considered by the investigator to have a relationship to study drug will be considered to be treatment-related AEs. If the investigator does not specify the relationship of the AE to study drug, the AE will be considered to be treatment-related.

The number of subjects with DLTs during the first cycle of study medication and the type of DLT will be listed.

An overall summary of AEs will include number (%) of subjects reporting any TEAEs, any DLTs in Cycle 1, any SAEs, any Grade 3 or 4 TEAEs, any treatment-related TEAEs, any fatal TEAE, any TEAEs leading to dose interruption/reduction/discontinuation, and any TEAEs leading to study discontinuation.

Number (%) of subjects reporting any TEAEs, any SAEs, any Grade 3 or 4 TEAEs, any treatment-related TEAEs, any treatment-related SAEs, any treatment-related Grade 3 or 4 TEAEs, any fatal TEAE, any TEAEs leading to dose interruption/reduction/discontinuation, and any TEAEs leading to study discontinuation will be tabulated by system organ class and preferred term. Number (%) of subjects reporting any TEAEs and any treatment-related TEAEs will be tabulated by preferred term in decreasing order of frequency in the overall column, and by system organ class, preferred term, and maximum severity.

9.4.3.2. Clinical Laboratory Tests

The SI unit will be used for all laboratory tests.

Laboratory test values outside the normal range will be assessed for severity based on the normal ranges for the clinical reference laboratory. The incidence of abnormal laboratory values and shift tables relative to baseline will be tabulated.

Laboratory data will be assessed for severity based on NCI CTCAE version 4.03. For specific laboratory parameters requiring clinical intervention to grade, the classification according to the quantitative component will be provided.

For numeric laboratory values, baseline value, postbaseline value, change from baseline, and percent change from baseline will be summarized by visit.

Shift summaries will be presented showing number and percentage of subjects with the laboratory values being low, normal, and high at baseline and at each of the scheduled postbaseline visits. The denominator for the percentage calculation will use the number of subjects in the baseline category (ie, low, high, normal, missing).

For the laboratory parameters that have CTCAE grading, shift tables will also be presented showing change in CTCAE severity grade from baseline to worst grade postbaseline. Separate tables will be provided for selected laboratory tests that have grading criteria in both high and low directions. All postbaseline values occurring within 30 days of last dose of study drug will be included when summarizing worst postbaseline grade. The denominator for the percentage calculation will be the number of subjects in the baseline category.

Categorical laboratory data will be tabulated by visit at baseline and postbaseline visits when necessary.

9.4.3.3. Vital Signs

Descriptive statistics and mean change from baseline will be determined for vital signs (blood pressure, heart rate, and body temperature) at each assessment time. Criteria for clinically notable vital sign abnormalities are defined in [Table 14](#). The abnormal values for subjects exhibiting clinically notable vital sign abnormalities will be listed.

Alert vital signs are defined as an absolute value outside the defined range and absolute percentage change greater than 25%. The abnormal values for subjects exhibiting alert vital sign abnormalities will be listed.

Table 14: Criteria for Clinically Notable Vital Sign Abnormalities

Parameter	High Threshold	Low Threshold
Systolic blood pressure	> 155 mm Hg	< 85 mm Hg
Diastolic blood pressure	> 100 mm Hg	< 40 mm Hg
Heart rate	> 100 bpm	< 45 bpm
Temperature	> 38°C	< 35.5°C

9.4.3.4. Electrocardiograms

Descriptive statistics and mean change from baseline will be determined for each ECG parameter at each assessment time. Average of all values before the first dose of study drug will be used as the baseline value. Criteria for clinically notable ECG abnormalities are defined in [Table 15](#).

The abnormal values for subjects exhibiting clinically notable ECG abnormalities will be listed.

Alert ECG values are defined as an absolute value outside the defined range and absolute percentage change > 25% (30% for QRS) interval. The abnormal values for subjects exhibiting alert vital sign abnormalities will be listed.

Outliers of QT, QTcB, and QTcF, defined as absolute values > 450 milliseconds or change from baseline > 30 milliseconds, will also be listed.

Table 15: Criteria for Clinically Notable ECG Abnormalities

Parameter	High Threshold	Low Threshold
QTcF	> 460 msec	< 295 msec
PR	> 220 msec	< 75 msec
QRS	> 120 msec	< 50 msec
QT	> 500 msec	< 300 msec
RR	> 1330 msec	< 600 msec

QTcF = Fridericia correction.

9.4.4. Other Analyses

█ [REDACTED]

█ [REDACTED]

- The PK parameters of INCB050465 and INCB039110 will be summarized by descriptive statistics by dose group and cohort. The log-transformed PK parameters of INCB050465 will be compared among the dose levels by using a 1-factor analysis of variance (ANOVA). Dose-dependent parameters (C_{max} and AUC) will be normalized to the lowest common dose before statistical comparisons. C_{max} and AUC will be evaluated using a power model, eg, $AUC = \alpha \cdot (\text{dose}^\beta)$ or equivalently, $\log(AUC) = \log(\alpha) + \beta \cdot \log(\text{dose})$, where linear dose proportionality is accepted if β is not significantly different from 1. Attainment of steady state will be assessed separately for each cohort by comparing trough plasma concentrations on Days 8 and 15 during Cycle 1.
- For the food-effect portion of the study, the log-transformed PK parameters of INCB050465 will be compared between the fed and fasted treatments using an ANOVA for a 1-way crossover design. The geometric mean relative bioavailability and 90% CIs will be calculated for comparing C_{max} and AUC between the fed (test) and fasted (reference) treatments.

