1.2.4. Clinical Summary of INCB050465

As of 02 SEP 2016, data were available for 46 subjects who received INCB050465 administered orally at QD doses of 5 mg (n = 1), 10 mg (n = 3), 15 mg (n = 3), 20 mg (n = 15), 30 mg (n = 20), and 45 mg (n = 4). The median duration of treatment was 104 days. Adverse events observed in $\geq 20\%$ of subjects were nausea, diarrhea, vomiting, neutropenia, fatigue, hypokalemia, and fever. No \geq Grade 3 treatment-related AEs were reported in $\geq 10\%$ of subjects. Serious AEs (SAEs) that occurred in ≥ 2 subjects included colitis (n = 3), diarrhea (n = 3), and pyrexia, pneumonia, dehydration, exfoliative dermatitis, and hypotension (n = 2 each). Eleven of the 46 subjects (24%) discontinued study treatment due to the following AEs: colitis, diarrhea, pneumonitis, rash, exfoliative dermatitis, psoriasis, neutropenia, pneumonia, and hypercalcemia. All but 1 of these events occurred after the 9-week disease assessment. No liver function test abnormalities > Grade 1 were reported while subjects were receiving study treatment. No dose-limiting toxicities were identified, and the maximum tolerated dose was not reached.

As of 02 SEP 2016, 20 objective responses as reported by investigators were observed at doses ≥ 10 mg QD in 41 evaluable subjects. Objective responses were observed in 5 subjects with DLBCL (n = 14), 6 subjects with follicular lymphoma (n = 6), 4 subjects with marginal zone lymphoma (n = 4); 3 subjects with mantle cell lymphoma (n = 4), 1 subject with Hodgkin lymphoma (n = 8), and 1 subject with CLL (n = 5). The objective response rate in evaluable subjects with NHL (n = 28) was 64%. Among the 18 objective responses observed in subjects with NHL, 17 (94%) were observed by the time of the first disease assessment.

Pharmacokinetics analysis showed the T_{max} is 0.5 to 1 hour, the terminal half-life is approximately 8 to 12 hours, and exposure appeared to be dose-proportional between 5 mg QD and 45 mg QD at steady state. The pharmacodynamic analyses demonstrated robust and sustained pathway inhibition at all dose levels tested. Refer to the [INCB050465 IB](#) for further details.

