Food effect was assessed in Part 3 Cohort A. Although coadministration of INCB050465 with a high-fat meal decreased 42% of dose-normalized C_{max} compared with the fasted state, it had mild effect on dose-normalized AUC (10% decrease) based on data from 12 subjects. The geometric mean ratio of AUC (fed vs fasted) and 90% confidence interval (CI) are 0.90 (0.68, 1.18), and INCB050465 may be administered without regard to meals (refer to the [INCB050465 IB](#)).

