9.3. Level of Significance

No hypothesis is being tested in the study. All CIs will be 95%.

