#### **3.2. Control of Type I Error**

All statistical analyses are exploratory in nature. Unless otherwise specified, all confidence intervals (CIs) provided will be at the 95% confidence level.

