### **7.3.4. Pharmacokinetic Analysis**

The PK calculations will be performed, if appropriate, using commercial software such as WinNonlin® (Pharsight Corporation, Mountain View, CA). Nominal times will be used in all cases, except when the difference between the actual time and nominal time is greater than 5 minutes for samples collected up to 4 hours after administration and greater than 15 minutes for samples collected more than 4 hours after administration; in these cases, actual time will be used for PK analysis. Additional details of analyses will be described in the SAP.

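### Protocol 9.4.4 concludes dose proportionality from a non-significant test of β = 1, so weak data support the conclusion more easily than strong data

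*Protocol*

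**What the plan says.** Protocol 9.4.4 plans three things for INCB050465 exposure across doses: descriptive statistics, a one-factor ANOVA of log-transformed parameters (Cmax and AUC dose-normalized), and a regression of log exposure on log dose. Of the last it says that Cmax and AUC "will be evaluated using a power model, eg" AUC = α·dose^β, and that "linear dose proportionality is accepted if β is not significantly different from 1".

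No significance level, margin or interval is given for β. Protocol 7.7.4 and Appendix B leave further PK detail to the SAP. SAP 7.3.4 then says "Additional details of analyses will be described in the SAP", which refers the reader back to the same document. The SAP contains no dose-proportionality method.

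Protocol 9.3 states "No hypothesis is being tested in the study. All CIs will be 95"%. SAP 3.2 states "All statistical analyses are exploratory in nature" and "Unless otherwise specified, all confidence intervals (CIs) provided will be at the 95% confidence level". The food-effect comparison, also in Protocol 9.4.4, is planned as a geometric mean ratio with a 90% CI.

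**The concern.** A non-significant test means only that the data are compatible with β = 1. They may be equally compatible with values well away from 1. If the true slope is not 1, wider scatter or fewer subjects makes non-significance more likely, so the rule rewards imprecision. The ANOVA in the same bullet does not help, because it has no margin either.

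PK is a secondary objective, and Cmax and AUC are secondary endpoints. A report that followed the plan could say proportionality was accepted while the data could not exclude a large departure over the dose range, and a reader would have no interval from which to see this. Protocol 1.2.4 already describes exposure as apparently proportional from 5 to 45 mg QD, without showing a slope, an interval or the method used.

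**Working it through.** The documents give no power, SD or margin for this test, so there is no stated figure to reproduce. The check is of how often the rule accepts when it should not.

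**Inputs from the documents.** Protocol 1.2.4 gives the 02 SEP 2016 allocation: 5 mg (1 subject), 10 mg (3), 15 mg (3), then "20 mg (n = 15), 30 mg (n = 20), and 45 mg (n = 4"). The total is 46 over a 9-fold dose range.

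**Assumptions.** One exposure value per subject; two-sided 5% test, suggested by the 95% CI default; CV of 20% to 50%, since no between-subject CV is given. The only hint is the food-effect result from 12 subjects, "The geometric mean ratio of AUC (fed vs fasted) and 90% confidence interval (CI) are 0.90 (0.68, 1.18"). If those data are paired:

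- half-width on the log scale = ln(1.18/0.68)/2 = 0.2756
- SE = 0.2756 / t(0.95, 11 df) = 0.2756/1.796 = 0.1535
- within-subject variance = 0.1535² × 12/2 = 0.1413
- CV = √(e^0.1413 − 1) = 39%

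This is a within-subject fed/fasted figure and only a proxy.

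**Information about the slope.** Mean ln(dose) = 3.148 and Sxx = Σ n(ln dose − mean)² = 8.457. Shares of Sxx are 28.0% for the single 5 mg subject, 25.4% for 10 mg and 20.5% for 45 mg. Those eight subjects hold 74%. The 35 subjects at 20 and 30 mg hold 4.1% + 15.1% = 19%.

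**Precision.** SE(β) = √ln(1 + CV²) / √Sxx. The 95% half-width is 2.015 × SE (44 df). If the estimate were exactly 1, the 95% CI for the 45 mg to 5 mg ratio of dose-normalized exposure would be 9^(±half-width).

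| CV | SE(β) | 95% half-width | CI for ratio when the estimate of β is 1 |
|---|---|---|---|
| 20% | 0.068 | 0.137 | 0.74 to 1.35 |
| 30% | 0.101 | 0.203 | 0.64 to 1.56 |
| 40% | 0.132 | 0.267 | 0.56 to 1.80 |

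**How often the rule accepts.** A true fold change F over 5 to 45 mg corresponds to β = 1 + ln F / ln 9, so 1.35-fold is β = 1.137 and 1.70-fold is β = 1.241. P(accept) = 1 − power of the noncentral t test with 44 df:

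| True departure | CV 20% | CV 30% | CV 40% | CV 50% |
|---|---|---|---|---|
| 1.35-fold | 50% | 74% | 83% | 87% |
| 1.70-fold | 7% | 35% | 57% | 69% |

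Simulation (200,000 runs per case) agrees to within 0.002.

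**Effect of sample size.** For β = 0.8 (dose-normalized exposure falls to 9^−0.2 = 64%), acceptance at CV 20/30/40/50% is 18/51/68/77% with 46 subjects. It is 36/66/78/84% with 16 subjects (one at 5 mg, three at each other dose).

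**Larger data sets at CV 40%** (assumed additions to the 46):

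| Scenario | 1.35-fold | 1.70-fold |
|---|---|---|
| +30 at 20 mg | 82% | 55% |
| +30 at 20 mg and +30 at 30 mg | 79% | 46% |
| every dose group doubled | 70% | 28% |

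Subjects added mid-range help little, because they contribute little to Sxx.

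**Could a formal equivalence rule pass?** With the 46 subjects and a true β of 1, the 90% CI for β falls inside 0.90 to 1.10 about 0.9% of the time at CV 20% and essentially never at CV 30% or more. By contrast, the Protocol's rule accepts 95% of the time when β = 1, at any CV.

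**The case against.** The strongest reply is about weight. Proportionality is not itself an objective or endpoint, the PK parameters are reported descriptively whatever β shows, the SAP calls every analysis exploratory, and no dose decision in the documents depends on this conclusion. All of that is right, and it keeps the point at the level of something that should be fixed, not something that threatens the trial. It does not defend the clause: an exploratory analysis is a reason to estimate, not to accept.

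A second reply is that the sizes rest on choices the documents do not make. The 1.35- and 1.70-fold departures are illustrative, and acceptance of the larger one runs from 7% to 69% with the CV. That also stands. At CV 20% the rule catches most 1.70-fold departures. The tables show the rule's behaviour and are not this trial's error rate.

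Third, 46 subjects is an interim cut against up to about 150 planned. Day 1 profiles from the INCB039110 combination subjects, Part 6 profiles and repeat profiles on Days 1 and 15 would add information, some of it at other dose levels. These were not modelled. They would lower the acceptance rates but would not supply the missing margin or interval.

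Finally, at exactly β = 1 the rule accepts 95% of the time whatever the sample size or scatter, so the claim that weaker data pass more easily applies only when β differs from 1. Those are the cases in which acceptance is an error.

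**Conclusion.** The clause is wrong as written. It permits a positive claim of dose proportionality with no margin and no required interval, and no other part of either document repairs it. With the 02 SEP 2016 allocation and a CV near 40%, it would accept a 1.35-fold departure about five times in six and a 1.70-fold departure more often than not. At that CV, even an estimated slope of exactly 1 would leave the 45 mg to 5 mg dose-normalized ratio anywhere from 0.56 to 1.80. These sizes depend on the assumed CV, a two-sided 5% level, one value per subject and the interim allocation. The logical fault does not. The consequence is an unsupported statement in the report on a secondary PK analysis. No effect on dose selection is claimed.

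A minor wording conflict goes with it: Protocol 9.3 rules out hypothesis tests and makes every CI 95%, while 9.4.4 uses a significance criterion and 90% CIs.

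**What to change.** 1. In Protocol 9.4.4, delete the clause that accepts proportionality on non-significance.
2. In its place, and in SAP 7.3.4 where Protocol 7.7.4 sends the reader, report β for Cmax and AUC with its CI, together with the implied ratio of dose-normalized exposure between the highest and lowest dose, (highest/lowest)^(β−1), with its CI.
3. Describe proportionality as not established when that interval includes departures the sponsor has stated beforehand to be material.
4. If a formal conclusion is wanted, judge the CI against limits the sponsor prespecifies and justifies. Because the 5 to 45 mg data had already been looked at by 02 SEP 2016, the plan should say when and on what grounds the limits were set. Limits of 0.90 to 1.10 on β would almost never be met with the 46-subject data, even if β = 1.
5. Amend Protocol 9.3 to allow CI levels other than 95% where specified, as SAP 3.2 already does, and reconcile its statement on hypothesis testing with 9.4.4.

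The model, data and sample size do not change. The cost is that proportionality can no longer be declared by default, and the honest result may be that the data do not settle it.

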9.5. Data Monitoring Committee

Not applicable.

9.6. Interim Analysis

Not applicable.

10. STUDY DRUG MATERIALS AND MANAGEMENT

10.1. Investigational Product Description – INCB050465

10.1.1. Packaging, Labeling, and Preparation of Study Drug

INCB050465 tablets are provided in high-density polyethylene bottles; no preparation is required. All bottles of Incyte investigational product contain the following language: "Caution: New Drug—Limited by Federal Law to Investigational Use."

10.1.2. Formulation and Chemical Properties of INCB050465

Physical and chemical properties of INCB050465 are summarized in the [INCB050465 IB](#). INCB050465 is formulated as 2.5 and 5 mg tablets (free-base equivalent). A tablet strength of 20 mg may also be used depending on the dose escalation of INCB050465.

10.1.3. Storage and Stability of INCB050465

INCB050465 drug product should be stored under ambient conditions at 15°C to 30°C (59°F to 86°F).

10.2. Investigational Product Description – INCB039110 (Comedication for Part 2 and Expansion Cohort E)

10.2.1. Packaging, Labeling, and Preparation of INCB039110

INCB039110 is provided in high-density polyethylene bottles of 35 tablets; no preparation is required. All bottles of Incyte investigational product contain the following language: "Caution: New Drug—Limited by Federal Law to Investigational Use."

10.2.2. Formulation and Chemical Properties of INCB039110

Physical and chemical properties of INCB039110 are summarized in the [INCB039110 IB](#). INCB039110 is formulated as 100 mg (free-base equivalent) SR tablets. (The 100 mg formulation is referred to in the [INCB039110 IB](#) as SR3.)

